3.3 Investigational Type

This is a post market, prospective, multicenter, 2:1 randomized study of the EnligHTN™ Renal Denervation System in conjunction with atrial fibrillation ablation. Up to one hundred subjects with paroxysmal or persistent atrial fibrillation and uncontrolled hypertension will be enrolled in the study. All subjects will undergo cardiac ablation for the treatment of atrial fibrillation. Per the 2:1 randomization, a minimum of 50 or 2/3 of the total patient cohort will also undergo renal artery ablation. Subjects will be followed up to years (2) years post procedure.

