5.7.7 Anticipated Serious Adverse Device Effect (ASADE)

A serious adverse device effect which by its nature, incidence, severity or outcome has been previously identified in the risk analysis report.

5.7.8 Procedure for assessing, recording and reporting adverse events, adverse device effects, serious adverse events and serious adverse device effects:

Safety surveillance and reporting will be done for all subjects enrolled in this investigation as described below.

Safety surveillance within this investigation and the safety reporting performed by the investigator, starts as soon as the subject is enrolled in this investigation (date of signature of the informed consent). The safety surveillance and the safety reporting will continue until the last

investigational visit has been performed or the subject is deceased or the subject/investigator concludes his participation into the investigation.

For the purpose of this trial, all Serious Adverse Events and all Adverse Device Effects (regardless of severity) are to be documented and reported to the sponsor immediately and this no later than 72 hours after becoming aware of the event.

Adverse events will be assessed by the investigator for relationship to the device and to the procedures involved.

- Procedure related: The AE is deemed related to the procedure if it occurred during the procedure but was not directly caused by the medical device.
- Device related: The AE is deemed device related if it was directly caused by the medical device.

Investigators are responsible for promptly reporting all SAEs and ADEs to the sponsor by completing the Adverse Event form. All unresolved AEs should be followed by the investigator until resolution is reached.

Note: Refer to Table 1 'Data Collection' and Appendix G 'Data Collection Method'. In case of EDC failure, notify Sponsor via Fax ([contact]) or via [contact].

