5.12.2 Investigation Conclusion

The investigation will be concluded when:

- A Close Out visit has been performed at each participating center AND
- The Final report has been provided by the sponsor

6 Risks and Benefits of the Clinical Investigation

Anticipated Adverse Events and Adverse Device Effects

Possible adverse events associated with the cardiac ablation procedure include, but are not limited to:

Cardiac Events:

- Abnormal ECG
- Angina (chest pain)
- Arrhythmia
- AV fistula
- Complete heart block
- Coronary artery injury
- Cardiac Perforation
- Cardiac Thromboembolism
- Myocardial infarction
- Obstruction/perforation/damage of the vascular system

- Death
- Dislodgement of implantable cardioverter defibrillator permanent pacing lead
- Endocarditis
- Exacerbation of pre-existing atrial fibrillation
- Heart Failure
- Hypotension heart block)
- Left atrial / esophageal fistula
- Pulmonary vein dissection
- Pulmonary vein stenosis

SJM CONFIDENTIAL AND PROPRIETARY

- Palpitation
- Pericardial effusion/cardiac tamponade
- Pericardial effusion without tamponade
- Pericarditis
- CHF exacerbation fluid overload
- Component damage to ICD or implantable pacemaker

- Pulmonary vein thrombus
- Temporary or complete heart block
- Unintended (in)complete AV, sinus node, heart block/damage
- Vessel wall/valvular damage or insufficiency
- Ventricular arrhythmia requiring defibrillation
- Bradycardia

Non-Cardiac Events:

- Air embolism
- Anesthesia reaction
- Cerebrovascular accident
- High creatinine phosphokinase (CPK)
- Infections
- Local hematomas / ecchymosis
- Laceration
- Phrenic nerve damage
- Pneumonia

- Pulmonary edema
- Pulmonary embolism
- Pulmonary hypertension
- Pleural effusion
- Pseudoaneurysm
- Respiratory depression
- Skin burns
- Syncope
- Transient ischemic attack
- Vasovagal reactions
- Vasovagal episodes

- Pneumothorax
- Vasospasm

Possible adverse events associated with the renal denervation procedure include, but are not limited to:

- Acute renal injury (renal infarction, renal hematoma)
- Renal vascular injury (renal artery dissection, renal artery thrombosis, renal artery stenosis)
- Collateral tissue injury
- Malignant or accelerated hypertension
- Symptomatic hypotension
- Access site complications (arteriovenous fistula, access site thrombosis, embolisation, pseudo-aneurysm, hematoma, limb ischemia, femoral nerve injury, or seroma)
- Disseminated intravascular coagulation

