#### 2.5.2 Safety Midterm (6 months) and Long term (1-2 years) data

For all patients, the major adverse cardiac events will be recorded and summarized at 6 months, 1 year, and 2 years. Event rates will be calculated for each arm as the number of subjects who experienced a major adverse cardiac event over the number of subjects who experienced an event within or were followed to each time interval. Kaplan-Meier analysis may be performed for time to first major adverse cardiac event. For patients undergoing the renal denervation procedure:

The new (or worsened) renal artery stenosis (>50%) and/or aneurysm at the site of

- ablation per Renal Artery Imaging will be summarized at 6 and 12 months. A percentage of patients who have new stenosis and/or aneurysm compared to baseline will be provided. The denominator includes subjects with a baseline and follow-up assessment at the corresponding interval. Image interpretation will be based on local analysis. Kaplan-Meier analysis may be performed if applicable on the time to the first new renal artery stenosis and/or aneurysm at the site of ablation.
- Renal function change based on eGFR will be summarized by computing the change of the eGFR at 6 months, 12 months and 2 years compared to baseline (follow-up interval baseline) for each patient with data available in both time points. The mean and standard deviation of the eGFR change at those intervals will be presented.
- Overall renal vascular safety will be summarized as a rate of subjects with a serious, device or procedure related event over total subjects randomized to the renal denervation group at each follow-up time point.

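### The SAP's overall renal vascular safety rate counts any serious device- or procedure-related event in the denervation arm, so it is not specific to renal vascular events, and its denominator is ambiguous

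*SAP*

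**What the plan says.** The third safety bullet of SAP 2.5.2 reads: "Overall renal vascular safety will be summarized as a rate of subjects with a serious, device or procedure related event over total subjects randomized". The denominator, given here in full because its last phrase matters, is "over total subjects randomized to the renal denervation group at each follow-up time point". The bullet stands under the lead-in "For patients undergoing the renal denervation procedure", which selects patients and does not describe events.

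The protocol adds the following:

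- Section 3.3: "All subjects will undergo cardiac ablation for the treatment of atrial fibrillation". Section 4.3 places randomization after that ablation is complete. Section 4.8 allows up to two repeat ablations over the 24 months.
- Section 5.7.8, on procedure relatedness: "The AE is deemed related to the procedure if it occurred during the procedure but was not directly caused by the medical device". Device relatedness is worded in the same general way. Neither definition says which of the two procedures, or which study device, is meant.
- Section 6.1 lists the anticipated denervation events. "Renal vascular injury (renal artery dissection, renal artery thrombosis, renal artery stenosis") is one category among many. Access-site complications, respiratory compromise and contrast allergy are listed separately.
- Section 3.2 measures renovascular safety by new renal artery stenosis or aneurysm at the ablation site. Section 7.4.2.2 does not contain the overall rate; it appears only in the SAP.

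**The concern.** A reader of the final report will take a rate labelled renal vascular safety as the proportion of denervation subjects with a serious renal vascular complication. The rule as written gives a different quantity: the proportion with any serious related event, whether from the AF ablation, a repeat ablation or denervation. A cardiac tamponade or a pulmonary vein stenosis, both listed in protocol 6.1 for cardiac ablation, would qualify. A complication arising during the index ablation precedes allocation and cannot be caused by denervation, yet it would count. The rate is specified for the denervation arm only, so no matching control-arm figure would show how much of it is AF-ablation background.

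The denominator raises a second, smaller question. The MACE rates in the same SAP section use subjects who had an event or were followed to the time point. The Primary Analysis population excludes denervation-arm subjects in whom the system never entered the body. A literal all-randomized denominator departs from both.

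**Working it through.** There is no planned figure for this rate to reproduce. SAP 2.2 states no event rates and no power calculation. The only related figure is the arm size: 75 × 2/3 = 50 under the SAP. At the protocol's 100 subjects it would be 100 × 2/3 = 66.7, about 67.

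**1. What the numerator admits.** The wording can be tested in two ways.

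- *Procedure and device unrestricted (the literal text).* AF-ablation complications, repeat-ablation complications, and all serious renal and non-renal denervation events count.
- *Procedure and device read as denervation only.* AF-ablation complications drop out. Serious access-site, respiratory or contrast events from protocol 6.1 still count.

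The numerator is wider than the label on either reading. The comma after the word serious also leaves open whether an event must be serious and related, or whether either suffices; the second would widen it further. In the other direction, a stenosis seen on imaging but not reported as a serious related event would be missed.

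**2. Size of the numerator effect.** Assumptions, none taken from the documents: n = 50; serious AF-ablation event rate c = 2-8%; renal vascular rate r = 0-2%; the two independent.

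With r = 0, expected subjects counted = n × c:

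- c = 2%: 50 × 0.02 = 1, so 1/50 = 2.0% (Clopper-Pearson 95% CI 0.05-10.6)
- c = 8%: 50 × 0.08 = 4, so 4/50 = 8.0% (2.2-19.2)
- Renal vascular events only: 0/50 = 0% (0-7.1)

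Chance that at least one such subject is counted = 1 − (1 − c)^50: 64% at c = 2%, 87% at 4%, 98% at 8%.

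With r = 2%, rate as written = 1 − (1 − r)(1 − c):

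- c = 2%: 1 − 0.98 × 0.98 = 3.96%. Share counted only for a non-renal event = (3.96 − 2)/3.96 = 49%.
- c = 8%: 1 − 0.98 × 0.92 = 9.84%. Share = (9.84 − 2)/9.84 = 80%.

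With about 67 denervation subjects and r = 0, the expected miscount is 67 × 0.02 = 1.34 to 67 × 0.08 = 5.36 subjects.

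**3. Size of the denominator effect.** Assume 5 of 50 randomized subjects were never treated or were lost, with 2 true events. All randomized: 2/50 = 4.0%. Had an event or were followed: 2/45 = 4.4%. The difference is 0.4 percentage points, downward.

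**The case against.** The best defence is contextual. The sentence concerns renal vascular safety and sits under a heading for denervation patients, so an analyst could supply the missing words and read procedure as denervation. The SAP never says that AF-ablation complications count; that follows from the missing restriction. This is fair, but it asks the analyst to repair the definition, and the narrower reading of procedure still admits non-renal denervation events.

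Four stronger readings are tempting and are not supported:

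- *The named secondary objective is measured wrongly.* It is not. The first bullet of the same SAP section reports new stenosis or aneurysm, with a denominator of subjects imaged at baseline and follow-up, and eGFR change has its own bullet. The rate at issue is supplementary and descriptive, with no test or decision rule attached.
- *The rate says nothing about renal vascular safety.* Serious related renal vascular events are included. The fault is lack of specificity.
- *Untreated and lost subjects are certainly counted as event-free.* The phrase about each follow-up time point can be read as limiting the denominator to those still present. The lead-in and the SAP 2.3 default to the Primary Analysis population also pull towards treated subjects. The text is ambiguous rather than clearly wrong.
- *The numerator and denominator errors might cancel.* In the illustration, 0.4 points downward does not offset 2 to 8 points upward.

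**Conclusion.** The point holds for this one supplementary rate. Its stated numerator is broader than its label, and applied literally it can report a non-zero renal vascular rate when no renal vascular event has occurred. On the assumed 2-8% rate of serious AF-ablation events and 50 subjects, that means 1 to 4 subjects. The size depends entirely on that assumption; the mismatch between label and numerator does not. The denominator needs clarifying, but its likely effect is minor. The imaging and eGFR analyses stand as planned. The change should be made before analysis, because the figure cannot be interpreted without it.

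**What to change.** Amend the third safety bullet of SAP 2.5.2:

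- **Numerator:** subjects with a serious renal or renal-artery event adjudicated as related to the denervation device or the denervation procedure. State that events must be both serious and related.
- **Denominator:** subjects in whom the denervation system entered the body and who had such an event or were followed to the time point. This matches the SAP's MACE rule and the Primary Analysis population.
- **Separate line:** all serious device- or procedure-related events, for both arms, so that the AF-ablation background is visible.

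The text change is small and needs no new patient assessments. It may not be wording alone. SAP 2.5.1 says serious and possibly related events are adjudicated, but neither document shows that attribution to a particular procedure or device is recorded, and the Adverse Event Adjudication Plan is not among the documents reviewed. If it is not recorded, the existing adjudicator would have to add it for what should be a small number of events.

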4.10.9 Renal artery evaluation

The renal artery evaluation will only be done in subjects who underwent the renal denervation ablation procedure.

Renal artery evaluation will be completed at the 6M and 12M follow-up visits. This evaluation can be completed by either: computed axial tomography (CT scan), duplex ultrasonography, Doppler, angiography, magnetic resonance (MR) angiography or non contrast magnetic resonance imaging.

If a renal artery evaluation is completed at any other time point during the study, this data will also be collected in the Renal Artery Evaluation CRF.

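### The 24-month renal vascular safety rate has no scheduled renal imaging behind it after month 12 and counts dropouts as event-free; it should be split at 12 months and labelled

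*SAP*

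**What the plan says.** **Imaging schedule.** Protocol Section 4.10.9 states: "Renal artery evaluation will be completed at the 6M and 12M follow-up visits". Tables 1 and 2 leave the 24-month cell blank. The same section restricts who is imaged ("The renal artery evaluation will only be done in subjects who underwent the renal denervation ablation procedure") and captures extra scans: "If a renal artery evaluation is completed at any other time point during the study, this data will also be collected". The protocol's long-term renovascular objective (Section 3.2) is set at 12 months.

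**Lesion measure.** In SAP Section 2.5.2, new or worsened stenosis above 50% and/or aneurysm at the site of "ablation per Renal Artery Imaging will be summarized at 6 and 12 months". Its denominator fits the imaging: "The denominator includes subjects with a baseline and follow-up assessment at the corresponding interval".

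**Overall measure.** The same SAP section adds a rate that Protocol Section 7.4.2.2 does not contain: "Overall renal vascular safety will be summarized as a rate of subjects with a serious, device or procedure related event over total subjects randomized". The denominator and timing read in full: "over total subjects randomized to the renal denervation group at each follow-up time point". Unlike the lesion bullet, it has no 6- and 12-month limit. Visits run to 24 months (Protocol Section 4.10).

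**Optional curve.** "Kaplan-Meier analysis may be performed if applicable on the time to the first new renal artery stenosis" and/or aneurysm. The SAP gives it no censoring rule and no end time.

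**The concern.** The overall rate will appear as one series at successive visits, and readers will take it as a time course. The means of finding a renal lesion change partway along it: two scheduled scans in year 1, none in year 2. If the series levels off after month 12, the reader cannot tell whether the arteries stayed healthy or were no longer examined.

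The study is descriptive, with no hypothesis test (SAP Section 2.2), so the reported percentage is itself the result. A 24-month renal vascular safety rate without qualification could be cited as evidence that the device leaves the renal arteries free of lesions at 2 years. The data collected cannot show that.

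The denominator pushes the same way. Every randomized subject stays in it at every time point, including those who left the study early.

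**Working it through.** **1. Can a silent lesion enter the numerator?** The rate is built from adverse events, so this must be traced through the protocol.
- Renal artery stenosis is listed as a possible adverse event of denervation (Section 6.1).
- An adverse device effect is any adverse event related to use of the device (Section 5.7.4).
- All such effects are reportable whatever their severity (Section 5.7.8).

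A silent stenosis seen on the 6- or 12-month scan and judged device related can therefore be reported and counted. The same lesion arising after month 12 needs symptoms, a fall in eGFR or an unscheduled scan before anyone knows of it.

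The numerator wording can be read in two ways: serious *or* related, or serious *and* related. On the second reading a silent lesion counts only if classed as serious, and the change at month 12 is smaller. The SAP does not say which reading applies, whether a scan finding alone counts, or whether the rate is cumulative.

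**2. Arm size.** SAP Section 2.2 gives 75 patients with two thirds denervated: 75 × 2/3 = 50, which reproduces its minimum of 50. With the protocol's approximately 100, 100 × 2/3 = 67. The documents state no rate for renal vascular safety.

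**3. Size of the detection gap.** Let a be the risk by 12 months, b the risk in year 2, and s the share of year-2 lesions found without scheduled imaging. If lesions count as events, the 24-month figure is a + s × b × (1 − a). All three inputs are assumptions. With a = 2%:

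| b | s = 0 | s = 0.25 | s = 0.5 | s = 1 |
|---|---|---|---|---|
| 1% | 2.0% | 2.2% | 2.5% | 3.0% |
| 2% | 2.0% | 2.5% | 3.0% | 4.0% |
| 4% | 2.0% | 3.0% | 4.0% | 5.9% |

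For example, with b = 2% and s = 1: 0.02 + 0.02 × 0.98 = 0.0396, or 4.0%. The shortfall runs from nothing (s = 1) to the whole year-2 risk (s = 0). The documents do not give s.

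**4. Denominator.** Assume 50 randomized, 2 events, and no events among dropouts. The planned rate is 2/50 = 4.0%. Over subjects who had an event or stayed in follow-up:
- 5% dropout: 2/47.5 = 4.2%
- 10% dropout: 2/45 = 4.4%
- 20% dropout: 2/40 = 5.0%

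The MACE rate in SAP Section 2.5.2 uses this second type of denominator. SAP Section 2.4 removes early exits from the AF recurrence rate expressly to avoid understating it.

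**5. Kaplan-Meier, if it is run.** Assume 50 in follow-up and 2 lesions first found at the 12-month scan. Keeping all 50 at risk gives 2/50 = 4.0%. Counting only those scanned gives 2/45 = 4.4% with 45 scanned and 2/35 = 5.7% with 35 scanned. If subjects stay at risk to study exit, only unscheduled imaging can move the curve after the 12-month scan.

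**The case against.** The strongest reply is that this is an adverse-event rate, not a lesion count. The SAP already confines lesion incidence to 6 and 12 months with an imaging-based denominator. Year-2 events are actively collected: serious adverse events and device effects are reported to the last visit, eGFR is measured at 24 months, and unscheduled renal scans are captured. On this view a footnote would be enough.

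Much of this stands. A reader might infer that the 24-month rate must equal the 12-month rate whatever happens in year 2, or that no year-2 lesion could be found. The documents do not support either, because the numerator can rise in year 2.

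The reply does not remove the point. Scan findings can enter the event rate in year 1, so ascertainment differs between the years within one series, and the SAP does not say so. The 24-month eGFR is a partial safeguard: the SAP summarizes it as a mean and standard deviation, and the protocol ties no renal imaging to an eGFR result.

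The MACE-type denominator is not neutral either. It keeps a subject who has an event and then leaves, but drops an event-free subject who leaves, so it can overstate the rate. It is still the convention the plan uses elsewhere, and mixing the two in one section is hard to defend.

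**Conclusion.** The point holds as a limit on what the 24-month rate can show. Silent renal artery lesions arising in year 2 are under-detected to an unknown degree, and the all-randomized denominator lowers the rate further. On an assumed 2% risk in each period, the 24-month figure could be anywhere from 2.0% to 4.0%. On 2 assumed events in 50, the denominator moves the rate from 4.0% to between 4.2% and 5.0%.

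This rests on reading the SAP's time points as including 24 months, which the bullet does not state but the section heading and visit schedule imply, and on scan findings being eligible as events. The Kaplan-Meier part applies only if that optional analysis is run.

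A reader might go further and call the 24-month figure falsely reassuring. That goes beyond the text: it is a legitimate rate of reported events and misleads only if read as 2-year freedom from lesions. Small numbers limit reassurance at any visit: with no events, the exact two-sided 95% upper limit is 1 − 0.025^(1/50) = 7.1% for 50 subjects and 5.4% for 67.

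**What to change.** In SAP Section 2.5.2:

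1. Report the overall renal vascular safety rate through 12 months as the imaging-supported figure. Report months 12 to 24 on a separate line labelled *adverse-event based; clinically detected or unscheduled imaging only; no scheduled renal imaging*, and state that it is not evidence of 2-year freedom from renal artery lesions.
2. Use the MACE-type denominator on both lines: subjects who had an event in the period or stayed in follow-up to its end.
3. In the same edit, state whether the numerator means serious or related events or only those that are both, whether it is limited to renal vascular events, whether a scan finding alone counts, and whether the rate is cumulative.
4. If the stenosis/aneurysm Kaplan-Meier curve is run, censor each subject at the last renal artery image and end the curve at the 12-month imaging window. Lesions found on later unscheduled scans go on the month 12 to 24 line.

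This costs SAP wording and one split table, with no new scans or patients. No data are discarded. The downside is that there is no single cumulative 2-year renal vascular safety figure.
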